## **Sensory Processing**

*SCAN-3: A Test for Auditory Processing Disorders in Adolescents and Adults*

<https://www.pearsonassessments.com/store/usassessments/en/Store/Professional-Assessments/Speech-%26-Language/SCAN-3%3AA-Tests-for-Auditory-Processing-Disorders-in-Adolescents-and-Adults/p/100000237.html>

*Brain-Body Center Sensory Scales (BBCSS)*

<https://www.phenxtoolkit.org/protocols/view/650401>

## **Quality of Life**

*Pediatric Quality of Life Inventory (PedsQL)*

<https://www.pedsql.org/>

**Case Report Forms:** this study employs both an electronic case report form system and a paper-based case report form system (i.e., source documentation records to support the EDC System).

## Appendix I. Table of Assessments

| Assessment  | Screening | V1 | V3 | V4 |
|---|-----------|----|----|----|
| Informed Assent/Consent   | X         |    |    |    |
| Demographics  | X         |    |    |    |
| Medical History Questionnaire and Screening   | X         |    |    |    |
| Autism Diagnostic Observation Schedule, 2 nd Edition (ADOS-2) or Autism Diagnostic Interview – Revised (ADI-R) – if needed   | X         |    |    |    |
| Wechsler Abbreviated Scale of Intelligence (WASI-II) – if needed  | X         |    |    |    |
| Medications, Screening  | X         |    |    |    |
| PsyToolkit's Eriksen Flanker and Wisconsin Card Sorting Tasks   |           | X  | X  | X  |
| SCAN-3:A Test for Auditory Processing Disorders in Adolescents and Adults   |           | X  | X  | X  |
| Dynamic Affect Recognition Evaluation (DARE)  |           | X  | X  | X  |
| Behavior Rating Inventory of Executive Function, Second Edition (BRIEF-2)   |           | X  | X  | X  |
| Mind Bender   |           | X  | X  | X  |
| Pediatric Quality of Life Inventory (PedsQL)  |           | X  | X  | X  |
| Brain-Body Center Sensory Scales (BBCSS)  |           | X  | X  | X  |
| Repetitive Behavior Scale - Revised (RBS-R)   |           | X  | X  | X  |
| Social Responsiveness Scale, Second Edition (SRS-2)   |           | X  | X  | X  |
| Social Skills Improvement System - Rating Scales (SSIS-RS)  |           | X  | X  | X  |
| Achenbach System of Empirically Based Assessment (ASEBA) - Age Dependent: Child Behavior Checklist (CBCL - parent report), Youth Self Report Form (YSR), Adult Self-Report (ASR), or Adult Behavior Checklist (ABC) |           | X  | X  | X  |
| Test of Adolescent Social Skills Knowledge (TASSK)  |           | X  | X  | X  |
| Medications, Since Last Visit   |           | X  | X  | X  |
| Adverse Effects   |           | X  | X  | X  |
| Unanticipated Adverse Effects   | As needed |    |    |    |
| Study Exit  | As needed |    |    |    |

## **Appendix II. Sample Debit Card Information**

Attached separately.

## **Statistical Analysis Plan**

CICADAS: Care Improving Cognition for Adolescents on the Autism Spectrum

Protocol Number: PSC-0909-20

NCT04562688

Document Date: November 9, 2021

To achieve robust and unbiased results, data will undergo a rigorous quality control process to ensure consistency in scoring, coding and accuracy of data entry. Standard data quality procedures will be used, including double scoring and random spot checking of assessments and electronic data capture. Additionally, 20% of all data folders will undergo a random audit every 3 months in Phase I. The database will be designed to not allow illegal values in entry. Any outliers will be double-checked with the raw data for accuracy.

#### Design and Analysis Populations

The Phase I data analysis plan *a priori* defines a primary intent-to-treat (ITT) population, a set of secondary evaluation populations, a set of primary outcome measures, a set of secondary outcome measures, five evaluation time points, a criterion for statistical significance, and a statistical analysis methodology for secondary outcomes.

There are four *a priori* defined analysis populations, including a primary analysis population (i), a secondary analysis population designed to compare effect sizes in populations with no missing data (ii), a population who completed all study visits (iii), and a population that was randomized to access CICADAS.

i. *Intent to Treat (ITT) population*: This is the *a priori* primary analysis population, defined as including all randomized participants who attended at least one PEERS session.

ii. *Intent to Treat (ITT) Fully-Evaluable (FE) population*: This is a secondary analysis population, defined as including all members of the ITT population that complete a post-intervention visit. Note that a participant may complete a specific visit but have missing data for a test in which case the participant is in the overall FE population but does not contribute data to the FE population for that visit, e.g., the number of evaluable cases for a specific test on a specific visit may be smaller than the FE population for that visit because of missing data.

iii. *Intent to Treat (ITT) Completers (C) population*: This is a secondary analysis population, defined as including all members of the ITT-FE population who complete all intervention sessions. Note that the C population is a strict subset of the FE population; a person who completes the treatment but does not complete the post-intervention evaluation visit is not a member of the C population.

iv. *Intent to Treat (ITT) CICADAS-Users (CU) population*. This is a secondary analysis population, defined as all members of the ITT population who have received CICADAS+PEERS, except those who drop/withdraw post-randomization and pre-treatment.

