### Description of Protocol Devices (Software Program)

This study employs three digital-device delivered interventions: CICADAS app, Active Control app, and PEERS. Participants assigned to receive CICADAS only will be engaged in NB-SCT exercises for a total of 40 hours during the 16-week period. Participants who are assigned to receive PEERS only will be engaged in weekly 1-hour PEERS group sessions led by a PEERS clinician during the 16-week period. Participants who are assigned PEERS + CICADAS will be engaged with the exercises for a total of 40 hours and weekly 1-hour PEERS group sessions during the 16-week period. Participants who are assigned PEERS + Active Control will be engaged with the Active Control app for a total of 40 hours and weekly 1-hour PEERS group sessions during the 16-week period.

Several elements of flexibility are allowed in the schedule to accommodate the challenges that adolescents with ASD may face:

- *Location of Use:* Some participants may experience barriers to receiving treatment, including geographic location, long waiting lists, and the requirement to take time off from school for clinic visits. This intervention is available either remote and/or in-person. Every effort will be made to schedule the weekly group sessions at a time that is most convenient for the participants. The assessments and exercises are digitally-accessible, allowing participants to complete them at different locations, as convenient.
- *Variable Number of Total Sessions:* Given fatigue (common in this population), commitments to non-study activities, health issues and/or reintegration into school, work and home life, we expect that some participants will not be able to complete the weekly PEERS sessions for 16 weeks. To accommodate this, we will be understanding of their circumstances, recommend that participants complete as many sessions as their schedule permits, and explain that the results of the trial may benefit from frequent and consistent involvement in group sessions. The site study coordinator may offer their support to work with the participant on a training schedule that is feasible, given participant's current life circumstances, as appropriate. To ensure a time-bounded study commitment, after 16 weeks such participants will perform their mid-intervention assessment (V3) or post-intervention assessment (*End of Study*, V4) visits, given that they have met the minimum number of sessions required to complete this visit.

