### Treatment Arms

**Arm A:** Participants assigned to Arm A will engage in CICADAS only for the first 16 weeks of the intervention period. After the completion of the first intervention period and the mid-intervention assessment (V3) visit, these participants will then be assigned to the PEERS only group for the second 16 weeks of the intervention period.

**Arm B:** Participants assigned to Arm B will engage in PEERS + CICADAS for the first 16 weeks of the intervention period. After the completion of the first intervention period and the mid-intervention assessment (V3) visit, these participants will then be assigned to No-Contact (no active intervention) for the second 16 weeks of the intervention period.

**Arm C:** Participants assigned to Arm C will engage in PEERS + Active Control for the first 16 weeks of the intervention period. After the completion of the first intervention period and the mid-intervention assessment (V3) visit, these participants will then be assigned to No-Contact (no active intervention) for the second 16 weeks of the intervention period.

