### Statistical Plan

Traditional Randomized Control Trials may not be the most effective way to test the efficacy of deeply-tailored, adaptive interventions. Instead, well-conducted, properly powered clinical trials that incorporate crossover design may be more useful in investigating how to optimize/enhance an evidence-based treatment (PEERS) with the experimental adjunct/primer (CICADAS). **Our trial defines: (1) three first stage treatment options; (2) a mid-study assessment point, (3) three second stage treatment options.**

After screening and enrollment, participants complete the full battery of assessments at baseline (Week 0). At Stage 1, **48** adolescents will be randomized to a 16 weeks of CICADAS only (Arm A) vs 16 weeks of PEERS + CICADAS (Arm B) vs 16 weeks of PEERS + Active Control. In order to reduce variance, we will employ a Stratified Permuted Block Randomization Design with strata defined by sensory processing symptoms to balance the number of individuals with SPA across each trial arm. After 16 weeks, the full battery of assessments will be administered again. Arms A, B and C will receive no contact for 16 weeks. At the end of the intervention, the full battery of assessments will be administered for a third time.

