### Primary Outcome - Feasibility

Efforts will be made to assess all participants who have completed the minimum required intervention activities: For Arm A (CICADAS only), completing at least 1 hour of NB-SCT; for Arm B (PEERS + CICADAS), completing at least one PEERS group session and 1 hour of NB-SCT; and for Arm C (PEERS + Active Control), completing at least one PEERS group session and 1 hour of games.

As the main goal of this Phase I trial is to evaluate the feasibility, acceptability and usability of the CICADAS app, we will conduct an analysis of the following primary outcome measures in all ITT-CU participants:

1. Digital assessments completion rate. We expect that  $\geq 80\%$  of participants will complete the digital assessment battery at least twice during the CICADAS intervention;
2. NB-SCT program adherence, that is automatically tracked on the back-end data portal (percentage of training sessions completed). Based on our previous studies (CLIMB, MOODIFY, WASABI) and pilot, we expect that  $\geq 70\%$  of participants will complete 20 hours of NB-SCT;
4. Reported side effects (raw score). Based on our previous findings, we expect 0 adverse events due to program use;

5. Overall program completion rate. Based on previous findings from CLIMB and from the pilot in ASD, we hypothesize full program completion in  $\geq 70\%$  study participants.

Secondary Outcome - Preliminary Efficacy

The secondary outcome measures will be collected by trained personnel blind to treatment assignment at baseline, half-way through the intervention, and immediately after the treatment for all randomized participants. Weekly measures will capture the number of initiated or reciprocated social gatherings related to or in addition to PEERS assigned social activities.

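### The primary ITT population requires a PEERS session, which Arm A cannot attend until after the 16-week CICADAS stage and V3, so Arm A is selected on an event that follows its week-16 outcome

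*SAP*

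**What the plan says.** SAP, Design and Analysis Populations, item (i), makes ITT the a priori population for the primary analysis, "defined as including all randomized participants who attended at least one PEERS session". No arm is exempted. Fully-Evaluable and Completers are nested in ITT. CICADAS-Users (CU) consists of ITT members who have received CICADAS plus PEERS, although the sentence introducing the four populations describes it as those randomised to access CICADAS. SAP, Primary Outcome - Feasibility, analyses the primary outcomes in CU.

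On Arm A's treatment, Protocol, Treatment Arms, says: "Participants assigned to Arm A will engage in CICADAS only for the first 16 weeks of the intervention period". After V3, "these participants will then be assigned to the PEERS only group for the second 16 weeks of the intervention period". General Study Design and Study Procedures/Research agree. SAP, Statistical Plan, says instead that after week 16 "Arms A, B and C will receive no contact for 16 weeks". Yet the SAP's exploratory comparison (b) uses the sequential delivery of CICADAS and then PEERS in Arm A.

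On assessment, SAP, Primary Outcome - Feasibility, says "Efforts will be made to assess all participants who have completed the minimum required intervention activities". For Arm A that minimum is one hour of training, with no PEERS. The protocol allows V3 or V4 after reduced participation "given that they have met the minimum number of sessions required to complete this visit". SAP, Evaluation Time Points, has outcomes collected on all participants, and the secondary-outcome text says all randomised participants.

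**The concern.** Entry to the primary population depends on something that happens after randomisation and that the arms can meet at very different times. For B and C it is one session at the start of treatment. For A it means staying through the whole CICADAS stage and V3, then starting a second programme. In comparison (a), B1-B2 against A1-A2, Arm A's outcome is measured before the event that decides whether the participant counts. In comparison (b), B1-B2 against A1-A3, Arm A is restricted to those who began the second component. Randomisation does not protect either comparison. The maximum-likelihood handling of missing data cannot help people whom the definition has removed.

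The primary feasibility outcomes are exposed too. The people most likely to show poor adherence to the stand-alone app leave the CU denominator, or Arm A is absent from it. Protocol, Sample Size Justification, says these data will power the Phase II trial and support a device submission, so a flattering rate would carry forward.

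**Working it through.** **1. The plan's own figure.** Protocol, Sample Size Justification: 48 completers, 15% non-completion, 56 recruited. 48 / 0.85 = 56.5, and 56 × 0.85 = 47.6, so 56 is consistent with 48. Per arm, 56 / 3 = 18.7. The SAP speaks of 48 randomised, which is 16 per arm. The protocol's 56 are recruited or consented, so using 56 as the number randomised is an assumption.

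**2. The rule applied to each documented schedule.**
- Protocol schedule: Arm A in ITT = n × (1 − q), where q is the share lost in stage 1. Anyone who attends V3 but never starts PEERS adds to the exclusions.
- SAP Statistical Plan sentence taken literally: Arm A in ITT = 0, so ITT is at most 32 of 48 (about 37 of 56).

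**3. Range for q.** The 15% covers the whole study, and its split by stage is not given. An even split gives q = 1 − √0.85 = 0.078. All of it in stage 1 gives 0.15. The pilot's attrition was above 30%, so 0.30 is used as a pessimistic value.

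**4. Possible shift in Arm A's mean change.** Suppose staying in has correlation r with the change score, both normal. Keeping only those who stay shifts the mean by r × φ(z_q) / (1 − q) SD, relative to a fully observed arm. The second factor is 0.158, 0.274 and 0.497 at the three values of q. The range r = 0.2 to 0.5 is an assumption.

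**5. Possible effect on CU adherence.** Assume true 20-hour adherence of 60% in A and B, every B participant attends one session, everyone lost from A in stage 1 is short of 20 hours, and the rest of A start PEERS. If CU is B plus those in A who reach PEERS, the CU rate is (2 × 0.60) / (2 − q).

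| q | Excluded of 18.7 | Excluded of 16 | Arm A left (18.7 / 16) | Shift, r = 0.2 to 0.5 | CU rate when truth is 60% |
|---|---|---|---|---|---|
| 0.078 | 1.5 | 1.2 | 17.2 / 14.8 | 0.03 to 0.08 SD | 62% |
| 0.15 | 2.8 | 2.4 | 15.9 / 13.6 | 0.055 to 0.14 SD | 65% |
| 0.30 | 5.6 | 4.8 | 13.1 / 11.2 | 0.10 to 0.25 SD | 71% |

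At q = 0.30 the last figure is 22.4 / 31.7, which passes the SAP's 70% target although the true rate is 60%. If CU means the concurrent combination only, it is Arm B alone. The stand-alone arm then has no primary feasibility analysis, although stand-alone use is one of the protocol's Specific Aims.

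**The case against.** The trial is a feasibility study. Its sample size is not driven by hypothesis testing, and the SAP says 48 participants cannot show an augmentation effect, so the comparisons with Arm A are exploratory. The SAP names ITT explicitly only for the baseline comparison that selects covariates; its use in the mixed model is inferred from its status as primary population. Arm A's one-hour assessment minimum suggests that nobody meant to exclude the arm. All of this stands, but that minimum governs who is assessed and does not amend the ITT definition. The exploratory status of the comparisons does not cover CU, which carries the primary outcomes.

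Three stronger readings are tempting and are not supported.

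- A reader might infer that excluded participants' outcomes are never collected. The SAP says outcomes are collected on all, or all randomised, participants. An Arm A member who trains for an hour and attends V3 meets the assessment minimum without PEERS. The protocol's session condition conflicts with those statements but does not settle the matter.
- A reader might infer that Arm A is certain to be empty. That rests on one SAP sentence, which contradicts three protocol sections and the SAP's own comparison (b).
- A reader might take the SD shifts as the bias caused by this rule. They compare those who stay with a fully observed arm. Many who leave in stage 1 would lack V3 data under any definition, and Arms B and C lose post-baseline data as well.

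**Conclusion.** The definition is wrong as written and should be corrected before analysis. It selects Arm A on an event after its week-16 outcome, while B and C are filtered only on one early session. Fully-Evaluable and Completers inherit the condition; CU inherits it and adds a PEERS requirement of its own.

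The size is about 1 to 6 of roughly 19 Arm A participants excluded, for stage-1 loss of 7.8% to 30%. For a given loss and correlation, the 0.03 to 0.25 SD shift is an upper bound on what the rule itself adds. Its own cost is the discarded baseline information and the discarded week-16 data of Arm A members who never start PEERS; the documents give no basis for sizing the latter. The adherence illustration crosses the 70% target only at the pessimistic end. The stage split, the correlation and the 60% adherence are assumptions. The comparison of B with C is little affected.

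**What to change.** - Define ITT as all randomised participants, analysed in the arm assigned, with no attendance condition.
- Define CU by randomisation to a CICADAS arm (A and B), with no PEERS condition, and report feasibility by arm. Redefining ITT alone would leave CU's own PEERS requirement in place.
- If a treated set is wanted, label it modified ITT, make it secondary, and use the arm-specific minima already in SAP, Primary Outcome - Feasibility.
- Reconcile the SAP Statistical Plan sentence on the second 16 weeks with Protocol General Study Design, Study Procedures/Research and Treatment Arms, and with SAP comparison (b).
- Reconcile the minimum-session condition for V3 and V4 (Protocol, Description of Protocol Devices and Withdrawal from the Protocol; SAP, Primary Outcome - Feasibility) with the statements that outcomes are collected on all participants. Invite every randomised participant who has not withdrawn consent to both visits.

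The cost is SAP wording, a short protocol edit and a few extra visits at $20 each (V4 is listed at about two hours). The downside is slightly less favourable feasibility rates and a slightly diluted treatment estimate.

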## General Study Design

We will employ a three-arm, active-controlled, randomized crossover trial to assess the safety and efficacy of CICADAS app in adolescents with ASD, and to evaluate its potential as a stand-alone treatment, as a primer for PEERS, or as a treatment enhancer of PEERS. We will randomize adolescents with ASD (ages 11-18) to CICADAS only, PEERS + CICADAS app, or PEERS + Active Control app.

Approximately 56 participants will be consented to ensure the successful completion of 48 participants (16 participants per treatment arm). A diagnostic interview will be performed to determine eligibility. Following inclusion and enrollment, participants will complete a set of assessments prior to the intervention to establish their baseline performance. Participants will then be randomized to the CICADAS only group (Arm A), PEERS + CICADAS app group (Arm B), or PEERS + Active Control app group (Arm C) and spend up to 16 weeks engaged in their assigned intervention. After 16 weeks, a full battery of assessments will be administered. For the next 16 weeks, Arm A will continue with PEERS only and Arms B and C will receive no treatment during this period. At the end of the intervention period, a full battery of assessments will be administered a second time to evaluate changes in performance. Finally, participants will be asked to fill out an online exit survey to rate enjoyment, usability, perceived benefits, and ease of fit into schedule.

During the first intervention period, participants assigned to the CICADAS only will complete NB-SCT exercises for 16 weeks. Participants assigned to PEERS + CICADAS will engage with the CICADAS app and complete weekly 1-hour PEERS group sessions for 16 weeks. Participants assigned to receive the PEERS + Active Control will engage in the Active Control app and complete weekly 1-hour PEERS group sessions for 16 weeks. During the second intervention period, participants assigned to receive PEERS only will complete weekly 1-hour PEERS group sessions for 16 weeks. During both intervention periods, these participants may have weekly electronic check-ins with site study personnel (as needed). The CICADAS app and the Active Control app icons, design and user experience will look the same as to not unblind the participants.

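### The population for the primary feasibility outcomes is defined inconsistently and, as written, selects on what participants do after randomisation

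*SAP*

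**What the plan says.** In the SAP, Primary Outcome - Feasibility, the plan states: "we will conduct an analysis of the following primary outcome measures in all ITT-CU participants". The outcomes listed there carry expected values: at least 80% for the digital assessments, at least 70% for 20 hours of training, at least 70% for programme completion, and no adverse events due to the program.

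The SAP section Design and Analysis Populations describes that set in two ways. Its opening list calls it "a population that was randomized to access CICADAS". Definition (iv) says it is "defined as all members of the ITT population who have received CICADAS+PEERS, except those who drop/withdraw post-randomization and pre-treatment". It is a subset of ITT, which is "defined as including all randomized participants who attended at least one PEERS session".

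The feasibility section also sets a minimum activity for assessing each arm. The Arm A minimum involves no PEERS: "For Arm A (CICADAS only), completing at least 1 hour of NB-SCT".

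The documents disagree on what Arm A receives in the second 16 weeks. The SAP, Statistical Plan, says: "Arms A, B and C will receive no contact for 16 weeks". The Protocol, General Study Design, says: "For the next 16 weeks, Arm A will continue with PEERS only and Arms B and C will receive no treatment during this period". The Protocol's Study Procedures/Research and Treatment Arms sections agree with the latter.

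**The concern.** A feasibility trial has to count the people who were offered the app and did not take it up. The defined set conditions on three things that happen after randomisation: attending a PEERS session, having received both treatments, and not leaving before treatment. It also conflicts with its own one-line description and with the Arm A minimum, so two analysts could build different primary data sets from the same text.

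Two separate things are at stake. One is the evidence on stand-alone use, which the Protocol's Specific Aims list first and which only Arm A provides. The other is whether the rates compared with the 70% and 80% expectations describe those assigned to CICADAS or only those who stayed long enough to enter the set.

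**Working it through.** **1. Who is in the set**

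| Reading | Arm A | Arm B |
|---|---|---|
| Opening list in the SAP | all randomised | all randomised |
| Definition (iv), SAP schedule (no contact in the second period) | nobody, because no PEERS is ever received | starters with at least one PEERS session |
| Definition (iv), Protocol schedule (PEERS in the second period), counting sequential receipt | only those still present to attend PEERS after the CICADAS period | starters with at least one PEERS session |

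No reading of definition (iv) gives the set in the opening list.

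**2. Sample sizes**

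Inputs: 48 completers, 15% non-completion and 56 recruited (Protocol, Sample Size Justification); 48 randomised (SAP, Statistical Plan); equal arms of 16 completers (Protocol, General Study Design).

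- The plan's own figure: 48/(1 − 0.15) = 56.5, so 57; or 48 × 1.15 = 55.2, so 56. The stated 56 is reproduced to within one. The primary outcomes have no power calculation to check.
- If 48 are randomised: 48/3 = 16 in Arm B, and 32 in Arms A and B.
- If 56 are randomised: 56/3 = 18.7, about 19 in Arm B; 2 × 56/3 = 37.3, about 37 in Arms A and B. The Protocol gives 56 as the number consented, before eligibility is settled, so this is the upper case.

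**3. Precision lost without Arm A**

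The upper bound with zero events is 1 − 0.05^(1/n), one-sided 95%. Intervals are exact (Clopper-Pearson) 95%, at the count nearest 70%. Sizes are before any non-starter is removed.

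| n | Zero-event upper bound | Count | Exact 95% CI |
|---|---|---|---|
| 16 (Arm B of 48) | 17.1% | 11/16 = 68.8% | 41.3–89.0% |
| 32 (A+B of 48) | 8.9% | 22/32 = 68.8% | 50.0–83.9% |
| 19 (Arm B of 56) | 14.6% | 13/19 = 68.4% | 43.4–87.4% |
| 37 (A+B of 56) | 7.8% | 26/37 = 70.3% | 53.0–84.1% |

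**4. Bias from removing non-starters**

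Let d be the share of those randomised who are removed without having met the target. Then rate among randomised = CU rate × (1 − d). The documents give no value for d. I take 5% to 15%, the top being the Protocol's projected total non-completion.

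| d (assumed) | CU rate 70% equals | CU rate 80% equals |
|---|---|---|
| 0% | 70.0% | 80.0% |
| 5% | 66.5% | 76.0% |
| 10% | 63.0% | 72.0% |
| 15% | 59.5% | 68.0% |

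In whole people, with 19 in Arm B and 2 who never start: 12/17 = 70.6%, but 12/19 = 63.2% of those randomised; 14/17 = 82.4%, but 14/19 = 73.7%.

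The formula is exact for non-starters, who cannot meet a completion target. It also fits people who quit everything before a first PEERS session. It does not fit someone who used the app fully but never attended PEERS; removing that person takes a success out of the app-adherence rate.

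**The case against.** The strongest reply is that this is a drafting slip. The opening list and the Arm A minimum suggest that Arms A and B were meant, and a users-only denominator is a legitimate choice for usability and the natural one for adverse effects. Both points are fair. They explain the text but leave the primary population undetermined. The SAP itself labels ITT-CU a secondary population, yet it is the only one named for the primary outcomes.

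Four stronger readings are tempting, and the documents do not support them.

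- *Arm A completion would be near 100% by construction on the sequential reading.* Staying in the study is not completing the app. The Protocol (Description of Protocol Devices) lets a participant stop using the program and remain, and the SAP asks only 1 hour of training before assessment. A low user who goes on to PEERS enters the set and misses the 20-hour target.
- *Everyone who disliked the app is removed.* An Arm B participant who starts, attends one PEERS session and then gives up stays in the denominator.
- *Adverse events outside the set go unrecorded.* Appendix I schedules adverse effects without restriction by arm, and the Protocol's section on serious adverse effects has staff ask about deterioration at each contact. Such events would be missing only from the primary-outcome summary.
- *The targets are a go/no-go rule.* The SAP words them as expectations and hypotheses, and the Protocol says the sample size is not driven by hypothesis testing.

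**Conclusion.** The point holds as an inconsistency in the primary analysis population combined with selection after randomisation. It should be fixed before analysis, because the text does not settle who is in the primary data set.

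The two consequences should be kept apart. Excluding Arm A removes the stand-alone evidence and roughly halves the sample, raising the zero-event upper bound from about 8–9% to about 15–17%. A reader might infer that this exclusion also inflates the rates. It does not by itself do so and could move them either way. The upward bias comes from dropping non-starters and those who quit before a first PEERS session. At an assumed 5% to 15%, a reported 70% stands for 66.5% down to 59.5% of those randomised, and there is no bias if everyone starts. The size rests on that assumption. The Protocol's report of more than 30% attrition in the earlier ASD pilot shows that dropout is a real concern here, but not how much of it precedes treatment.

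**What to change.** - Define the primary feasibility set as all participants randomised to Arms A and B, and make the opening list and definition (iv) agree.
- Count non-starters and dropouts as non-completers for the completion and adherence outcomes.
- Report each rate pooled and by arm, with exact 95% confidence intervals.
- Summarise adverse effects in everyone in Arms A and B who opened the app, beside Arm C.
- Keep the current users-only set as a supportive analysis.
- Reconcile the Arm A second-period schedule between the SAP's Statistical Plan and the Protocol's General Study Design, Study Procedures/Research and Treatment Arms sections. Which schedule applies is for the sponsor to state.

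The cost is SAP wording. Training adherence is already logged automatically and adverse effects are already collected in all arms, so no new data are needed. The downside is that the completion figures may look less favourable.
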